Insomnia Dry mouth, dysgeusia, diarrhea, constipation DSMP We are starting with the lowest possible dose available and increasing to a maximum dose comparable to the highest Qsymia dose (15mg) evaluated, and less than 50% of the highest available dose (37.5mg); DSMP (including blood pressure heart rate, review of systems, and physical exams at every study visit). Individuals who meet inclusion criteria and have well-controlled hypertension, must have a cardiac echocardiogram reviewed by Cardiology within the prior 6 months before the initiation of phentermine, consistent with the Children's Colorado Lifestyle Medicine clinical protocol. Rare, but Serious DSMP (including blood pressure, heart rate, review of systems, and physical exams at every study visit). Individuals who meet inclusion criteria and have well-controlled hypertension, must have a cardiac echocardiogram reviewed by Cardiology within the prior 6 months before the initiation of phentermine, consistent with the Children's Colorado Lifestyle Medicine clinical protocol. Tolerance, Diversion potential (without clear evidence of withdrawal) ⁴⁵ Short duration of intervention may reduce risk of tolerance.	Restlessness, Irritability, Anxiety	enrollment, and at every study visit; Prompt mental health evaluation/management available			
Dry mouth, dysgeusia, diarrhea, constipation We are starting with the lowest possible dose available and increasing to a maximum dose comparable to the highest Qsymia dose (15mg) evaluated, and less than 50% of the highest available dose (37.5mg); DSMP (including blood pressure, heart rate, review of systems, and physical exams at every study visit). Individuals who meet inclusion criteria and have well-controlled hypertension, must have a cardiac echocardiogram reviewed by Cardiology within the prior 6 months before the initiation of phentermine, consistent with the Children's Colorado Lifestyle Medicine clinical protocol. Rare, but Serious DSMP (including blood pressure, heart rate, review of systems, and physical exams at every study visit). Individuals who meet inclusion criteria and have well-controlled hypertension, must have a cardiac echocardiogram reviewed by Cardiology within the prior 6 months before the initiation of phentermine, consistent with the Children's Colorado Lifestyle Medicine clinical protocol. Tolerance, Diversion potential (without clear evidence of withdrawal) ⁴⁵ Short duration of intervention may reduce risk of tolerance.	Dizziness	DSMP			
We are starting with the lowest possible dose available and increasing to a maximum dose comparable to the highest Qsymia dose (15mg) evaluated, and less than 50% of the highest available dose (37.5mg); DSMP (including blood pressure heart rate, review of systems, and physical exams at every study visit). Individuals who meet inclusion criteria and have well-controlled hypertension, must have a cardiac echocardiogram reviewed by Cardiology within the prior 6 months before the initiation of phentermine, consistent with the Children's Colorado Lifestyle Medicine clinical protocol. Rare, but Serious DSMP (including blood pressure, heart rate, review of systems, and physical exams at every study visit). Individuals who meet inclusion criteria and have well-controlled hypertension, must have a cardiac echocardiogram reviewed by Cardiology within the prior 6 months before the initiation of phentermine, consistent with the Children's Colorado Lifestyle Medicine clinical protocol. Tolerance, Diversion potential (without clear evidence of withdrawal) ⁴⁵ Short duration of intervention may reduce risk of tolerance.	Insomnia				
available and increasing to a maximum dose comparable to the highest Qsymia dose (15mg) evaluated, and less than 50% of the highest available dose (37.5mg); DSMP (including blood pressure, heart rate, review of systems, and physical exams at every study visit). Individuals who meet inclusion criteria and have well-controlled hypertension, must have a cardiac echocardiogram reviewed by Cardiology within the prior 6 months before the initiation of phentermine, consistent with the Children's Colorado Lifestyle Medicine clinical protocol. Rare, but Serious DSMP (including blood pressure, heart rate, review of systems, and physical exams at every study visit). Individuals who meet inclusion criteria and have well-controlled hypertension, must have a cardiac echocardiogram reviewed by Cardiology within the prior 6 months before the initiation of phentermine, consistent with the Children's Colorado Lifestyle Medicine clinical protocol. Tolerance, Diversion potential (without clear evidence of withdrawal) ⁴⁵ Available and increasing to the highest days the highest han 50% of the highest days the highest han 50% of the highest han 50%		DSMP			
DSMP (including blood pressure, heart rate, review of systems, and physical exams at every study visit). Individuals who meet inclusion criteria and have well-controlled hypertension, must have a cardiac echocardiogram reviewed by Cardiology within the prior 6 months before the initiation of phentermine, consistent with the Children's Colorado Lifestyle Medicine clinical protocol. Tolerance, Diversion potential (without clear evidence of withdrawal) ⁴⁵ DSMP (including blood pressure, heart rate, review of systems, and physical exams at every study visit). Individuals who meet inclusion criteria and have well-controlled hypertension, must have a cardiac echocardiogram reviewed by Cardiology within the prior 6 months before the initiation of phentermine, consistent with the Children's Colorado Lifestyle Medicine clinical protocol. Short duration of intervention may reduce risk of tolerance.		available and increasing to a maximum dose comparable to the highest Qsymia dose (15mg) evaluated, and less than 50% of the highest available dose (37.5mg); DSMP (including blood pressure, heart rate, review of systems, and physical exams at every study visit). Individuals who meet inclusion criteria and have well-controlled hypertension, must have a cardiac echocardiogram reviewed by Cardiology within the prior 6 months before the initiation of phentermine, consistent with the Children's			
review of systems, and physical exams at every study visit). Individuals who meet inclusion criteria and have well-controlled hypertension, must have a cardiac echocardiogram reviewed by Cardiology within the prior 6 months before the initiation of phentermine, consistent with the Children's Colorado Lifestyle Medicine clinical protocol. Tolerance, Diversion potential (without clear evidence of withdrawal) ⁴⁵ Teview of systems, and physical exams at every study visit). Individuals who meet inclusion criteria and have well-controlled hypertension, must have a cardiac echocardiogram reviewed by Cardiology within the prior 6 months before the initiation of phentermine, consistent with the Children's Colorado Lifestyle Medicine clinical protocol. Short duration of intervention may reduce risk of tolerance.	Rare, but Serious				

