Title: Adjunctive Anti-Obesity Pharmacotherapy in Adolescents and Young Adults after Bariatric Surgery: A Randomized Controlled Pilot Study

NCT#: NCT04095104

Document Version Date: 07/21/2021

COMIRB Protocol

COLORADO MULTIPLE INSTITUTIONAL REVIEW BOARD [name] [contact] [contact]

Protocol #: 18-2793

Project Title: Adjunctive Anti-Obesity Pharmacotherapy in Adolescents and Young Adults after

Bariatric Surgery: A Randomized Controlled Pilot Study

Principal Investigator: [name]

Co-Investigators: [name]; [name] PhD; [name]; [name]

Version Date: 7/21/21

I. Hypotheses and Specific Aims:

Primary Aim 1: Assess the feasibility (including protocol implementation and acceptability) of a randomized, placebo-controlled, double-blinded, adjunctive 12-week phentermine + topiramate intervention beginning 6-12 months after bariatric surgery, among adolescents and young adults (age 12-24 years) who don't achieve expected weight loss or who remain severely obese (n=14 total). **Hypothesis 1**: Protocol implementation, including recruitment and retention, will be feasible based on achievement of adequate enrollment and participant completion of at least 80% of study visits. The experimental group will report better acceptability compared to the control group based on satisfaction with the desired effects of the active drugs.

Secondary Aim 2: Test the initial efficacy of standard of care plus 12 weeks of active drugs or placebo on percent weight loss beginning 6 to 12 months postoperatively.

Hypothesis 2: The experimental group will experience a greater percent weight loss than the control group at the end of the 12 week intervention period.

Secondary Aim 3: Evaluate the initial effects of standard of care plus 12 weeks of active drugs or placebo on cardiometabolic, eating behavior, and quality of life outcomes beginning 6 to 12 months postoperatively.

Hypothesis 3: The experimental group will demonstrate greater improvements than the control group in blood pressure (BP), lipids, alanine aminotransferase (ALT), hemoglobin A1c (HbA1c), and fat mass reduction; and, will report less hunger, increased satiety, more cognitive restraint, decreased daily caloric intake, increased resting metabolic rate, and better quality of life at the end of the 12 week intervention period.

II. Background and Significance:

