Unpublished latent class growth trajectory modeling data from our group of the Teen-LABS³² participants 5 years after Roux-en-Y Gastric Bypass (RYGB) or Sleeve Gastrectomy (SG) demonstrate significant heterogeneity in surgical response. Where ≥ 20% BMI loss is considered to be an adequate response, among adolescents who had RYGB, 16% achieved only a 5% BMI loss and another 21% achieved a 16% BMI loss at 5 years. Among those who had SG, 36% achieved only a 7% BMI loss at 5 years postoperatively. Additionally, greater %BMI loss at 6 months postoperatively was associated with a more successful 5-year BMI trajectory. These data further underscore the need for adjunct treatment options for a sizeable subset of adolescents within the first year after bariatric surgery.

The Bariatric Surgery Center at Children's Hospital Colorado³³, led by Drs. [name] (Surgical Director) and [name] (Medical Director), began seeing patients in June 2017. Patients undergo either SG or RYGB. Over the last 25 months, patient volume has accelerated, and currently there are 103 patients in the program (Mean age: 17 [Range: 10-36]; Female: 73%; Race/Ethnicity: 46% Hispanic, 27% Non-Hispanic White, 14% Black, 13% Other). Based on a chart review of current postoperative patients who have had surgery ≥6 months ago, we estimate that 2 patients per month will meet inclusion criteria for this study. Therefore, we anticipate that 14 patients will be eligible for enrollment during the proposed 7-month recruitment timeline (Table 2). This allows for a 29% reduction in eligible individuals from the combination of upfront decline and dropout to successfully meet the target sample size of 10. This does not account for projected increases in overall Bariatric Surgery Clinic patient volume over the proposed timeline.

The patented combination pill phentermine/topiramate XR (trade name Qsymia) is generally not covered by Colorado insurance plans and costs ~\$200/month out of pocket, which makes it inaccessible for the vast majority of our patient population. We, like other pediatric weight management programs, prescribe phentermine and *immediate release* topiramate as individual medications (~\$30/month). This research proposal was designed to mimic this usual practice of prescribing individual phentermine and immediate release topiramate pills, which will allow for a more realistic assessment of feasibility and increases generalizability.

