Fourteen patients (7/arm) followed in the Children's Hospital Colorado Bariatric Surgery Center who meet inclusion criteria: 12-24yo; s/p SG or RYGB; and at 6-12 months post bariatric surgery^a, have either a) not achieved mean expected weight loss based on national standards and still have at least class 1 obesity or b) remain severely obese (\geq 120% of 95%ile or BMI \geq 35kg/m2 for 12-17yo; BMI \geq 35kg/m2 for 18-24yo) will be randomized 1:1 to pharmacotherapy + SOC^b or placebo + SOC in double-blind fashion. Expected weight loss at 6, 9, and 12 months postoperatively will be defined as a \geq 26%, \geq 28%, and \geq 31% decrease in weight, respectively, from preoperative weight (within 1 week of surgery) as was observed in the Teen-LABS study.⁷

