- There will be a screening visit at 6, 9, or 12 months postoperatively. Eligible participants will be consented at this visit, and will be asked to come to campus ~1 week later for study visit 1. Enrollment and Visit 1 cannot be combined because it is unrealistic to screen, consent, randomize, obtain study drug, and complete additional measures after an already lengthy clinical appointment.
- The Children's Hospital Colorado Lifestyle Medicine weight management program's clinical protocols for anti-obesity pharmacotherapy require monthly clinic visits for the first three months after initiation for monitoring of effects and side effects. The proposed study protocol follows this standard.

Data Collection Tools (See Table 3. below for Schedule of Measures)

- a) Sociodemographic characteristics: age, sex, race/ethnicity, insurance, highest level of primary caregiver's education, household size and income, government-based assistance, and presence/absence of food insecurity will be obtained from the medical record and the Demographics Form.
- b) Feasibility of protocol implementation: rates of recruitment, enrollment, randomization, and dropout
- c) Study medication adherence & tolerability: assessed by 1) Questionnaire: description/dose/start date of medications, missed doses, and checklists of: effects, adverse effects, and evidence-based barriers to adherence^{51,52}; 2) Pill counts; 3) Urine amphetamine screen
- d) Self-reported changes to all non-study medications: name/dose, interim changes
- e) Patient/family satisfaction questionnaire will assess: reasons for participation, experience during study visits, satisfaction with the effect of the study medication/placebo, ease of communication with study staff, and time burden/inconvenience
- f) Biological outcome and safety measures: Weight, height, heart rate (HR), BP, basic metabolic panel, lipids, ALT, HbA1c, and pregnancy test
- g) Optional Biobanking: Gold top (serum-3.5mL blood), Purple top (EDTA-4mL whole blood), Green top (heparinized plasma-4mL blood), and Urine (volume that remains after the urine pregnancy test for females and a separate urine collection for males) will be collected with participant assent/consent for future research questions.
- h) 3-day dietary record: Participants will complete a dietary record on 3 consecutive days (2 weekday, 1 weekend day) based on standardized protocols for dietary assessment.⁵³

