In addition to the above in-person study visits and designated remote data collection, there are eight standard study phone calls in the protocol:

- Phone Call 1: 1-2 days before the Screening/Enrollment Visit 0 (Reminder to fast)
- Phone Call 2: 1 week before Visit 1 (Phone Call Script 1)
- Phone Call 3: 1 week after Visit 1 (Phone Call Script 2)
- Phone Call 4: 2 weeks after Visit 1 (Phone Call Script 2)
- Phone Call 5: 3 weeks after Visit 1 and 1 week before Visit 2 (Phone Call Scripts 1 & 2)
- Phone Call 6: 1 week before Visit 3 (Phone Call Script 1)
- Phone Call 7: 1 week before Visit 4 (Phone Call Script 1)
- Phone Call 8: 1 week after last dose of study drug (Phone Call Script 2)

If a participant requires additional dose titration during the protocol, the PI will conduct additional weekly phone calls until study medication dosage is stable.

E. Potential Scientific Problems:

Benchmarks for success, pitfalls, and alternatives:

Primarily, we expect this protocol to demonstrate feasibility, which will form the foundation for a larger study of pharmacotherapy as an adjunct to bariatric surgery. Secondarily, we expect to demonstrate short-term efficacy of pharmacotherapy in terms of promoting additional weight loss and improving biological markers.

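### Do the two uses of 10 patients conflict, and does the enrollment criterion in Hypothesis 1 need a number?

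*Combined protocol and SAP*

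**What the plan says.** Section III (Preliminary Studies) estimates two eligible patients a month and says "we anticipate that 14 patients will be eligible for enrollment during the proposed 7-month recruitment timeline". It then allows for "a 29% reduction in eligible individuals from the combination of upfront decline and dropout to successfully meet the target sample size of 10", and adds: "This does not account for projected increases in overall Bariatric Surgery Clinic patient volume over the proposed timeline".

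The other counts are these:

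- Section I, Aim 1, describes the population as those "who don't achieve expected weight loss or who remain severely obese (n=14 total".
- Section IV.B begins "Fourteen patients (7/arm) followed in the" hospital's bariatric center and randomizes them 1:1.
- Section IV.B also gives 20 as the number of local subjects needed to answer the question, with patients and parents or guardians counted separately.
- Section IV.F (sample size justification) names 10, five per arm, as the minimum. It takes 25% as a realistic dropout rate and gives precision at 10 and at 14 participants, accepting both.

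Hypothesis 1 says protocol implementation "will be feasible based on achievement of adequate enrollment and participant completion of at least 80% of study visits". Only the visit criterion carries a number. The part of Section IV.E headed "Benchmarks for success, pitfalls, and alternatives" adds none for enrollment. The Aim 1 analysis in Section IV.F reports the rates of recruitment, enrollment, randomization and dropout, with no cut-off.

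**The concern.** The same 10 seems to be counted at two stages: after decline and dropout in Section III, before dropout in Section IV.F. If 10 are randomized and a quarter leave, 7.5 are expected to remain, so a trial at the Section IV.F minimum would miss the Section III target. Section IV.F blurs the stages further by twice calling the result of its dropout calculation an enrollment rate.

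Feasibility is the primary aim, and one of its two criteria has no threshold. Suppose 11 are randomized and 3 drop out, leaving 8. That meets a minimum of 10 randomized, misses 14, and misses 10 remaining. If the count that matters can be picked once the data are in, the verdict on Hypothesis 1 can be picked too.

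**Working it through.** **Inputs.** Two eligible patients a month for 7 months, and a target of 10 (Section III). Dropout of 25%, minimum of 10, and stated dropout precision at n = 10 of 13 points (68% confidence) and 20 points (90%) (Section IV.F). Planned size 14 (Sections I and IV.B). The plan gives no separate decline rate.

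**1. The plan's figure.** 2 × 7 = 14 eligible. 1 − 10/14 = 28.6%, which rounds to the stated 29%. It reproduces.

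**2. If dropout in Section III means loss after randomization.**
- Randomized patients needed for 10 remaining: 10/(1 − 0.25) = 13.33.
- Room for decline: 14 − 13.33 = 0.67 of a patient, or 0.67/14 = 4.8%.
- No declines: 14 × 0.75 = 10.5 remain, a loss of 25%.
- One decline: 13 × 0.75 = 9.75 remain, a loss of 1 − 9.75/14 = 30.4%.

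So one decline misses the target by 10 − 9.75 = 0.25 of a patient in expectation. In whole patients, 13 randomized with 3 dropouts (3/13 = 23%) leaves exactly 10. Treating dropouts as independent at 25%, the binomial chance that at least 10 remain is 0.06 with 10 randomized, 0.58 with 13 and 0.74 with 14.

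**3. If it means loss between consent and randomization.** Section IV.D says eligible patients consent and then "will be asked to come to campus ~1 week later for study visit 1". Under the eConsent route, enrollment also depends on screening blood work and, for females, a pregnancy test. Losses in that window are plausible. On this reading 14 − 4 = 10 are randomized, which agrees with Section IV.F.

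**4. Which 10 Section IV.F uses.** Half-width = z × √(p(1 − p)/n).

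| p and n | 68% | 90% |
|---|---|---|
| 25%, n = 10 | 13.6 | 22.5 |
| 2 of 10 | 12.6 | 20.8 |
| 25%, n = 13.33 | 11.8 | 19.5 |
| stated for n = 10 | 13 | 20 |

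The wording applies dropout to 10 participants, and the 68% figure fits n = 10, not 13.33. The 90% figure does not separate the two. The same calculation is given for 14 participants, so the precision statement does not depend on how the Section III forecast is read.

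**5. The enrollment criterion.** As shares of the 14 projected eligibles, 10 randomized is 10/14 = 71% and 14 randomized is 100%. These are the two candidates. Hypothesis 1 covers retention separately through its 80%-of-visits criterion, so a count after dropout is not a natural meaning of enrollment, and Section III is a forecast, not a success rule. In the example of 11 randomized and 3 lost, the open question is therefore only whether 11 is judged against 10 or 14. The 20 subjects in Section IV.B would equal 10 patients if each had one parent counted, which is an assumption.

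**The case for a change.** The best case for a change is that enrollment and dropout are primary outcomes, that the results are meant to plan a later trial, and that the repair is a text edit needing no patients, visits or analyses. On the plain reading of Section III, an allowance described as covering decline and dropout covers little more than dropout. Randomizing 14 would take every projected eligible patient unless clinic volume grows or the adult-program fallback in Section IV.E is used, and neither is quantified.

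Part of this stands. No section links 10 or 14 to adequate enrollment, so 10 to 13 randomized can be called success or shortfall. The enrollment label in the dropout calculation is wrong, and the Section III sentence is loose.

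The consequences do not stand. The label is a slip that the sentence itself exposes, since it starts from an observed dropout rate. No part of the plan promises 10 completers from 10 randomized. It is also too strong to say no threshold can be inferred: Section IV.F names 10 as the minimum for this aim and Aim 1 states 14. A threshold fixed before unblinding would protect little, because study staff see enrollment counts throughout while still blinded to treatment.

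**Conclusion.** No change to the plan follows. On one reading of an undefined word, the forecast is short by a quarter of a patient once a single patient declines; on the other there is no conflict. This rests on the plan's 25% dropout and on a forecast of 14 that is a rough monthly rate, leaves out growth in clinic volume and has a fallback source of patients. No analysis, precision figure, power or type I error uses the forecast.

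The missing enrollment figure is an unwritten definition affecting only results of 10 to 13 randomized. Because Aim 1 is descriptive and gives each rate separately, analysts can report the number randomized against both the minimum of 10 and the planned 14, and readers can judge. Which of the two should count as adequate is itself debatable, so fixing one would tidy the wording without changing what is estimated or reported.
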